Protocol Title:

Evaluation of the Compuflo Epidural Instrument for Thoracic Epidural Space Identification

NCT Number: NCT03376256

Document Date: February 20, 2018

Objectives:

Purpose of this pilot study is to evaluate whether this injection pump technology, which is FDA approved for lumbar epidural anesthesia, is also capable of identifying the thoracic epidural space through measurement of pressure levels. While this device is approved by the FDA for use in the procedure of the lumbar epidural, it is not actually used to perform the epidural procedure but rather to measure the epidural pressure. This study will likewise measure the epidural pressure.

Background:

A successful and safe performance of epidural anesthesia/analgesia in the perioperative setting relies on correct identification of the epidural space (ES) by the operator. Multiple methods for objective and more or less simple identification of the ES have been proposed such as waveform analysis (1), nerve stimulation (2), fiber optical or ultrasound guidance (3,4), and acoustic signal assistance (5).

However, none of these suggested techniques is currently standard of care and most anesthesiologists and/or pain physicians still utilize the subjective manual feeling of a loss of resistance (LOR).

Consequently, reported epidural failure rates using LOR for ES identification vary greatly and can range for instance for labor epidural analgesia from 1.5% up to 23%, if a standardized definition of epidural failure is applied (6,7). Failure rates for epidural analgesia for postoperative pain management after major surgery are even higher and can reach up to 27% for lumbar and 32% for thoracic epidurals (8).

Previously, the now FDA approved Compuflo Epidural Instrument has been demonstrated to successfully and safely identify the lumbar epidural space. This technology allows for real-time pressure readings at the epidural needle tip, which are displayed in digital and graphical fashion.

This study is designed to evaluate this technology for ES identification when performing thoracic epidural anesthesia.

Patients will receive thoracic epidural anesthesia in the following fashion:

After attaching American Society of Anesthesiologists standard monitors, patients will be placed in a sitting position. Following disinfection and preparation in the usual fashion, an epidural Tuohy needle will be introduced at a thoracic level 0 to a depth of approximately 3cm. The epidural Tuohy needle will then be connected to a 3-way stopcock with a loss of resistance syringe filled with normal saline connected to the in-line port and the Compuflo Epidural Instrument connected to the side-port. The stopcock will be turned “Open” to the LOR syringe and “Close” to the Compuflo Epidural Instrument. The operator will then advance the epidural Tuohy needle until a loss of resistance is perceived. The stopcock will then be turned “Open” to the Compuflo Epidural Instrument and “Close” to the LOR syringe. The Compuflo Epidural Instrument will be started at an infusion rate of 0.050ml/sec of normal

saline for 30 seconds. The pressure readings will be graphically and digitally recorded.

The Compuflo Epidural Instrument will then be stopped and the stopcock will be disconnected from the Tuohy needle. After disconnection of the epidural Tuohy needle, an epidural catheter will be advanced at the discretion of the operator. After removal of the epidural needle and securing of the epidural catheter, a 3 mL epidural test dose consisting of lidocaine (15 mg/mL) with epinephrine (5 mcg/mL) will be given to rule out intrathecal or intravascular catheter position. Epidural anesthesia will then be established at the discretion of the operator by dosing the epidural catheter with a local anesthetic of their choice and a volume of their choice. Fifteen to thirty minutes after dosing the epidural catheter a blinded investigator will assess the patient for sensory and motor blockade. Successful performance of epidural anesthesia will be defined as a loss of sensation to cold in at least one dermatome, either unilateral or bilateral. If an epidural catheter cannot be advanced into the epidural space, the epidural Tuohy needle will be withdrawn to a depth of 3cm or completely removed and inserted at a new puncture site and a new attempt of epidural Tuohy needle insertion and identification of the epidural space with the loss of resistance technique will begin. After a maximum of 3 failed attempts, epidural space identification will be considered unsuccessful

Phase B – Thoracic Epidural Space Identification with the Compuflo Epidural Instrument:

Patients will receive thoracic epidural anesthesia in the following fashion:

After attaching American Society of Anesthesiologists standard monitors, patients will be placed in a sitting position. Following disinfection and preparation in the usual fashion, an epidural Tuohy needle will be introduced at a thoracic level o to a depth of approximately 3cm. The epidural Tuohy needle will then be connected to a 3-way stopcock with a loss of resistance syringe filled with normal saline connected to the in-line port and the Compuflo Epidural Instrument connected to the side-port. The stopcock will be turned “Close” to the LOR syringe and “Open” to the Compuflo Epidural Instrument. The Compuflo Epidural Instrument is started and set to infuse normal saline at a rate of 0.050ml/sec with a pressure limit of 100mmHg. The operator will then slowly advance the epidural Tuohy needle until the Compuflo Epidural Instrument indicates that the ES has been reached. This is achieved by observation of a drop of pressure of at least 50mmHg sustained for at least 5 seconds (“low pressure plateau”). The Compuflo Epidural Instrument will then be stopped and the stopcock will be turned “Close” to the Compuflo Epidural Instrument and “Open” to the LOR syringe. Once the operator has confirmed correct ES identification with the LOR syringe, the stopcock will be disconnected from the Tuohy needle.

After disconnection of the epidural Tuohy needle, an epidural catheter will be advanced at the discretion of the operator. After removal of the epidural needle and securing of the epidural catheter, a 3 mL epidural test dose consisting of lidocaine (15 mg/mL) with epinephrine (5 mcg/mL) will be given to rule-out intrathecal or intravascular catheter position. Epidural anesthesia will then be established at the discretion of the operator by dosing the epidural catheter with a local anesthetic of their choice and a volume of their choice. Fifteen to thirty minutes after dosing the

epidural catheter a blinded investigator will assess the patient for sensory and motor blockade. Successful performance of epidural anesthesia will be defined as a loss of sensation to cold in at least one dermatome, either unilateral or bilateral. If an epidural catheter cannot be advanced into the epidural space, the epidural Tuohy needle will be withdrawn to a depth of 3cm or completely removed and inserted at a new puncture site and a new attempt of epidural Tuohy needle insertion and identification of the epidural space with the loss of resistance technique will begin. After a maximum of 3 failed attempts, epidural space identification will be considered unsuccessful.

Follow up:

Patients will be evaluated in a timeframe of 12h-24h after epidural catheter removal for potential complications. A sensory and motor exam will be performed. Patients will also be evaluated for any symptom of post-spinal-puncture headache. Patients who did not receive epidural anesthesia due to inability to identify the epidural space will be evaluated in the same fashion in a timeframe of 12-24h after attempted epidural anesthesia.

Data collection:

Data will be collected on case report forms. Demographic data of each patient (weight, height, age, gender) will be recorded at the beginning of each case. Pressure readings from the Compuflo Epidural Instrument will be recorded once the epidural space is reached in Phase 1 of the study, and throughout the procedure in Phase 2. Success rate of epidural anesthesia and complications will be recorded.

Data will be stored in individual study folders and locked in a Division of Regional Anesthesia faculty office.

Data management

Demographical data and pressure readings will be analyzed by calculating a mean and standard deviation. Success rates and incidence of complications will be recorded in percentages and a median including 25th to 75th percentile range will be calculated.

Risks/ Benefits

In Phase 1 of the study, there will be no personal direct benefit and minimal risk for harm since the Compuflo Epidural Instrument will be solely used for the purpose of measuring pressures while the actual performance of thoracic epidural anesthesia will be with the traditional LOR method.

In Phase 2 of the study, the patient may directly benefit from the more objective identification method of the epidural space with the Compuflo Epidural Instrument. A potential risk is electrical failure of the computerized injection pump; in such case, the operator will revert back to the traditional LOR technique.

Setting:

Research consents will be obtained in the operating room holding area of the University of Miami Hospital or Jackson Memorial Hospital, as applicable, for patients admitted the day of the procedure. In hospital patients will be consented

the night prior to the procedure in their admitted locations. This study will take place at University of Miami Hospital or Jackson Memorial Hospital.

Resources available:

[name] is a Professor of Clinical Anesthesiology and Director of the Division of Acute Pain Medicine and Regional Anesthesia in the Department of Anesthesiology, Perioperative Medicine and Pain Management at the University of Miami Miller School of Medicine. He has conducted substantial previous research as the principal investigator in multiple clinical trials in the area of acute pain and regional anesthesia. [name] will be responsible for overseeing the recruitment, consent, collection and storage of data as well as performing the measurements described in the procedure section.

[name] is an Assistant Professor in Clinical Anesthesiology and in the Division of Acute Pain Medicine and Regional Anesthesia. She has participated in investigator-initiated research and authored manuscripts in anesthesiology previously and is well versed in research compliance.

The study coordinators are experienced in conducting clinical research for clinical trials and investigator-initiated studies. They will assist the investigators in study-related activities.

Patient Recruitment Methods:

Potential subjects will be identified by the study team based on the scheduled procedures to be done by the Regional Anesthesia team. Patients on the schedule will be pre-screened using available medical data for exclusion criteria. If patients do not meet any of

the exclusion criteria they will be visited by the Principal Investigator, Sub-investigator and/or Study coordinators on the morning of surgery or the night before depending on their admission status. If the subject is currently an inpatient at the hospital, the medical team taking care of the patient will be approached by the study team to get permission to approach the subject. Study details, risks, benefits and alternatives will be discussed with each potential subject. If the patient shows interest into the study, the PI will notify research personnel of potential participant to start the process of consent. Study information and informed consent document (attached) will be provided to each subject. If the patient agrees to the study a copy of the signed consent will be provided to the patient and one placed in the patient medical chart. The original document will be placed in the study specific subject folder.

Local number of subjects:

A total of 20 patients will be expected to be enrolled into this pilot study.

Confidentiality:

Data will be recorded on study sheets locked in a Division of Regional Anesthesia faculty office in a locked filing cabinet for the period of one year. Additionally, data will be stored on a password protected University of Miami computer in the Department of Anesthesiology in [name]. Only study personnel listed on the IRB protocol will have access to the data. All study records and documents, will be retained for studies that are subject to both

FDA and HIPAA regulations: According to HIPAA regulations will be retained for a minimum of six years following study closure. Our research department will retain all research data until the later of these dates. The data will be destroyed after this time in accordance with university policies.

Consent process:

Written informed consent will be obtained for each subject in English-speaking subjects only. Subjects who do not speak English will not be enrolled. Research consent will be obtained in the operating room holding area of University of Miami Hospital for patients admitted the day of the procedure. In hospital patients will be consented the night prior to the procedure in their admitted locations.

Patient's identity and age will be verified prior to obtaining informed consent, as well as their understanding of risks and benefits and possible alternatives available explained before any informed consent signature from those patients willing to participate. The PI(s) with each study participant will:

- Ensure each patient is given full and adequate oral and written information about the nature, purpose, possible risk, and benefit of the study.
- Ensure each patient is notified that they are free to discontinue from the study at any time.
- Ensure that each patient is given the opportunity to ask questions and allowed time to consider the information provided.
- Ensure each patient provides signed and dated ICF before conducting any

procedure specifically for the study.

- Ensure the original, signed ICF(s) is/are stored in the investigator's Study File.
- Ensure a copy of the signed and dated ICF is given to the patient for future reference of the study.
- Ensure that any incentives for patients who participate in the study as well as any provisions for patients harmed as a consequence of study participation are described in the ICF that is approved by an IEC/IRB.

All potential subjects will be given ample time to review the consent form and discuss any questions and concerns with research personnel or study doctor, and will be provided with a copy of the signed ICF. Consent will be documented with a dated signature on the consent form from both the patient and the study personnel conducting the consent discussion.

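### Second- and third-attempt successes count in full and no attempt record is listed, so in Phase B a device miss rescued by loss of resistance can pass as success in the device phase

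*Combined protocol and SAP*

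**What the plan says.** The retry rule closes the Phase A and the Phase B procedure text in the same words. The stated trigger is "If an epidural catheter cannot be advanced into the epidural space, the epidural Tuohy needle will be withdrawn to a depth of 3cm", or is removed and reinserted elsewhere, and the rule ends with "After a maximum of 3 failed attempts, epidural space identification will be considered unsuccessful". No other trigger for a new attempt is given.

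In Phase B, as in Phase A, the repeat is described as a new needle insertion after which "identification of the epidural space with the loss of resistance technique will begin". Read literally, the device has one attempt in Phase B and any repeat is by loss of resistance (LOR). The Risks/Benefits section adds that the operator reverts to LOR if the pump fails electrically.

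The success definition carries no condition on attempt or method: "Successful performance of epidural anesthesia will be defined as a loss of sensation to cold in at least one dermatome, either unilateral or bilateral".

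Under Data collection the outcome item is "Success rate of epidural anesthesia and complications will be recorded", alongside demographics and pressure readings. Attempt number, the method used on each attempt and how each attempt ended are not listed. Under Data management, "Success rates and incidence of complications will be recorded in percentages and a median including 25th to 75th percentile range will be calculated", with no split by attempt.

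**The concern.** The stated purpose is to learn whether pressure readings can identify the thoracic epidural space. That is a property of a single needle attempt guided by a given method. The planned result is a property of the patient after up to three attempts. A space found on the third attempt at a new puncture site scores the same as one found at once.

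In Phase B the two are further apart, because the method changes after the first attempt. A patient in whom the device signal led to a catheter that would not advance, and in whom LOR then worked, is still a Phase B patient with a successful epidural. The plan has no rule that attributes the success to LOR, and no listed data item that would show it. At stake is the main thing a pilot of 10 patients per phase can supply for a later study: how often the device signal is right the first time. The extra needle passes also go uncounted, although they bear on how any complications are read.

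**Working it through.** The plan gives no expected success rate and no sample-size reasoning, so there is no figure of its own to reproduce. The per-attempt rates below are assumptions shown over a range.

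**Inputs.** Maximum of 3 attempts (both procedure sections). Phase B repeats by LOR (Phase B section). 10 patients per phase (Procedures Involved). The Background gives up to 32% failure for thoracic epidurals; it is used only as a convenient value, because it is an upper figure for failed postoperative analgesia and not a rate per needle attempt.

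**Phase B: one device attempt, then up to two LOR attempts.** With device success d and LOR success r per attempt, and independent attempts:

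success within three = 1 − (1 − d)(1 − r)²

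| Device first-attempt success d | r = 50% | r = 68% | r = 80% |
|---|---|---|---|
| 0% | 75.0% | 89.8% | 96.0% |
| 30% | 82.5% | 92.8% | 97.2% |
| 50% | 87.5% | 94.9% | 98.0% |
| 70% | 92.5% | 96.9% | 98.8% |

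For the first row: 1 − 0.32² = 0.898 and 1 − 0.20² = 0.960. A device that never worked would give at least 9 successes in 10 patients with probability 73% (r = 68%) or 94% (r = 80%). Moving the device from 0% to 70% raises the reported figure by 7.2 points at r = 68% and by 2.8 points at r = 80%. First-attempt success would move by 70 points.

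**Phase A: up to three LOR attempts.** With miss rate m per attempt and independent attempts, failure = m³ and the chance of no failure in 10 patients = (1 − m³)¹⁰.

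- m = 15%: 0.15³ = 0.3%; chance of no failure 97%.
- m = 32%: 0.32³ = 3.3%; chance of no failure 72%, although 10 × 0.32 = 3.2 first-attempt misses are expected.
- m = 50%: 0.50³ = 12.5%; chance of no failure 26%.

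At 68% first-attempt success, the chance of at least 9 of 10 is 12% when first attempts are counted and 96% under the three-attempt rule.

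**Correlated attempts (Phase A form).** Attempts in one patient share anatomy and probably the operator. With a beta distribution of miss rates across patients, k = (1 − ρ)/ρ, a = mk, b = (1 − m)k:

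failure = a(a+1)(a+2) / [(a+b)(a+b+1)(a+b+2)]

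For m = 0.32, ρ = 0.1: k = 9, a = 2.88, failure = 2.88 × 3.88 × 4.88 / (9 × 10 × 11) = 5.5%, so success within three is 94.5% rather than 96.7%. At ρ = 0.3 it is 89.4%. With m = 0.40 the figure falls from 93.6% (independent) to between 90.6% and 84.3%. The gap from the first-attempt rate shrinks but stays wide.

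**The case against.** Several stronger readings are tempting, and the documents do not support them.

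- *The attempt number will not be collected.* The case report form is not part of the documents. Only the absence from the listed data is established. Phase B pressures are recorded throughout the procedure and may show some repeats, but no count is planned and an LOR repeat need not leave a device trace.
- *Repeated false device signals are absorbed in Phase B.* As written, the device has one attempt, so cubing a single miss rate does not describe that phase. The retry wording matches Phase A and might have been carried over. If device repeats are intended, the Phase A formula applies instead.
- *A false end-point that lets the catheter thread is never detected.* Phase B requires LOR confirmation before the catheter is advanced, and the recorded success needs cold loss found by a blinded investigator. A threaded catheter with no block fails that measure. Neither check shows on which attempt, or by which method, a success came.
- *Almost any method would score near 100%.* At 50% per attempt the within-three figure is 87.5%, and correlation lowers it.

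It is also fair that Phase A first-attempt performance describes LOR rather than the device. Attempt number still has some use there: the 30-second pressure run comes before the catheter is tried, so readings from an attempt that then failed could be averaged with the rest unless they are labelled.

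Finally, this is a descriptive pilot with no test and no named primary endpoint, and precision is low whichever outcome is used: 7 of 10 has an exact 95% interval of about 35% to 93%. That stands. It limits how much the study can say, but it is no reason to report a percentage that mixes two methods.

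**Conclusion.** The concern holds as a matter of reporting and attribution. Both procedure sections allow up to three attempts before identification is called unsuccessful, and neither Data collection nor Data management separates successes by attempt or method. Phase B is the serious case: if LOR repeats succeed 68% to 80% of the time, a device with no first-attempt success would still be accompanied by about 90% to 96% success in its own phase. If repeats succeed only half the time, the figure is 75%. In Phase A the masking is real but smaller, and depends on the assumed miss rate and on correlation.

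These sizes rest on assumed per-attempt rates, on independence where stated, and on reading the Phase B retry literally. A reader might infer that the planned success rate carries no information about the method, or that the retry rule is itself at fault. Neither follows. The rate carries limited information, and the weakness lies in what is listed for recording and reporting.

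**What to change.** 1. Add one case report form line per attempt: attempt number, method used (device or LOR), and ending (no signal, signal not confirmed, catheter would not advance, catheter advanced). A switch to LOR after pump failure would then show in the method field.
2. In Data management, report for each phase first-attempt success by that phase's assigned method, with an exact confidence interval, beside success within three attempts. State whether success here means catheter advanced or cold loss obtained. Giving both is preferable, since the block also depends on the drug and volume the operator chooses.
3. State that in Phase B a success reached by an LOR repeat is not counted as identification by the device.
4. Confirm that the Phase B retry wording is as intended, so that the attribution rule matches practice.

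The clinical retry rule is left as it is. The cost is one form line per attempt and a few sentences of text, with no change to procedures or patient numbers. The downside is a less favourable percentage with a wide interval.

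### The three-attempt rule labels catheter failure as failed space identification, and does not define a failed attempt

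*Combined protocol and SAP*

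**What the plan says.** The Objectives section asks whether the instrument can identify the thoracic epidural space from pressure.

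Under Procedures Involved, each phase describes how the space is reached. In Phase A: "The operator will then advance the epidural Tuohy needle until a loss of resistance is perceived". In Phase B the sign is "observation of a drop of pressure of at least 50mmHg sustained for at least 5 seconds", followed by a check with the syringe: "Once the operator has confirmed correct ES identification with the LOR syringe, the stopcock will be disconnected from the Tuohy needle".

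Both phases then use the same repeat rule. It opens with "If an epidural catheter cannot be advanced into the epidural space". The needle is withdrawn or re-sited, and "a new attempt of epidural Tuohy needle insertion and identification of the epidural space with the loss of resistance technique will begin". The rule closes with "After a maximum of 3 failed attempts, epidural space identification will be considered unsuccessful".

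The Follow up section provides for "Patients who did not receive epidural anesthesia due to inability to identify the epidural space". Success of epidural anesthesia is a separate outcome, defined by loss of cold sensation in one or more dermatomes. The Data collection section lists demographics, pressure readings, the success rate of epidural anesthesia and complications.

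**The concern.** The event that starts a repeat is a catheter that will not advance. The label given after three failures is about finding the space. These are different events, and the study is about the second.

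Two things follow. First, a patient in whom the space was signalled and confirmed can still end as an identification failure because of the catheter. Second, the failures of most interest have no written next step: no loss of resistance, no plateau, or a plateau that the syringe does not confirm. With no definition of a failed attempt, two operators could count the same sequence of passes differently and both be following the protocol.

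At stake is whether the pilot can say in how many patients the instrument found the space. The items listed under Data collection do not include the number of attempts or why each one ended. On that list, the two kinds of failure could not reliably be separated afterwards. The case report form itself is not in the documents, so it may hold more.

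**Working it through.** The documents give no power, alpha or derived sample size on this point, so there is no stated figure to reproduce. The check is mainly of the text.

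**Step 1. List how an attempt can end and what the protocol writes for each ending.**

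| How the attempt ends | Phase | Written next step | Counts towards the 3? |
|---|---|---|---|
| No loss of resistance perceived | A, and LOR repeats in B | None | Not specified |
| No pressure plateau | B, instrument pass | None | Not specified |
| Plateau, not confirmed by LOR | B, instrument pass | None | Not specified |
| Space signalled (and confirmed in B), catheter will not advance | A and B | New attempt by LOR | Yes, by the repeat rule |
| Catheter advanced | A and B | Test dose, dosing, sensory check | Not a failure |

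The only failure with a written next step is the fourth row. After three of these the patient receives the label in the closing sentence, although the space was signalled each time.

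**Step 2. Look at the method used on repeats in Phase B.** The repeat rule specifies LOR in both phases. If it is followed as written, a Phase B patient who reaches three attempts has had one by the instrument and 3 − 1 = 2 by LOR. The label would then rest mostly on attempts that did not use the instrument to find the space.

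**Step 3. Size.** Inputs: 10 patients per phase (Procedures Involved); success reported as percentages (Data management).

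- One patient reclassified: 1/10 = 10 percentage points of that phase's identification rate.
- Illustration, with exact (Clopper-Pearson) 95% intervals: 10/10 gives 69.2% to 100%; 9/10 gives 55.5% to 99.7%; 8/10 gives 44.4% to 97.5%. If nine patients are identified with a catheter placed and the tenth falls in the fourth row, the label as written gives 9/10. Counting identification by itself gives 10/10.
- Chance of at least one such patient in a phase: 1 − (1 − p)^10. The per-patient rate p is not in the documents. Assumed values of 2%, 5% and 10% give 18%, 40% and 65%.

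**Step 4. Effect on the cold-sensation success rate.** A patient whose space was never found and a patient whose catheter never passed both end without an established epidural. Provided both are handled alike in that rate, moving a patient between the two categories changes it by 0 points.

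**The case against.** The strongest reply is that the rule reads sensibly as a whole. The cap sentence is not restricted to catheter failures. An attempt is described as needle insertion together with identification, so a pass that never finds the space is naturally a failed attempt. A catheter cannot enter a space that was not reached. The Follow up section also foresees patients in whom the space could not be identified.

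This largely stands. A reader might infer that passes without a signal fall outside the cap and may be repeated without limit, or that the label leaves out non-detection altogether. The documents do not say either. What they leave open is whether such passes count.

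A second reply is that the label may be a deliberately cautious definition: a space that never accepts a catheter is not accepted as identified. Plateau plus LOR is not proof of position. The Background calls LOR subjective, and the value of the pressure signal is what the pilot is testing. That is a tenable definition, but the protocol does not state it. It would also still merge two kinds of failure that the sponsor will want to tell apart.

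Third, the recorded success outcome is anesthesia by cold sensation, and Data management names no identification rate. This is correct and limits the size: the 10 points apply only to an identification rate if one is reported.

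Finally, a reader might expect complications to be related to the number of passes. The plan does not promise that analysis, and its absence is not part of this point.

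**Conclusion.** The point holds as a defect of classification. In both phases the written trigger (catheter will not advance) and the assigned label (space not identified) refer to different events, and a failed attempt is undefined. A patient with a signalled and confirmed space can therefore be classed as an identification failure, and it is unspecified whether passes with no signal or no confirmation count.

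The size is 10 percentage points per affected patient in a per-phase identification rate, and nothing in the cold-sensation success rate. This rests on 10 patients per phase, on an identification rate being reported because identification is the stated objective, and on the rule being applied as worded. How often such a patient would occur is not known from the documents; the 18% to 65% range depends entirely on the assumed rates.

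It does not invalidate the pilot. It is an inexpensive change that helps the study answer its own question.

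**What to change.** - **Wording.** Reconcile the attempt sentence and the label sentence in Phase A and Phase B so that they refer to the same event, and define a failed attempt. The clinical limit stays with the sponsor.
- **Recording.** Add one case report form line per attempt, giving the method (instrument or LOR) and why the attempt ended: no plateau; no LOR; plateau not confirmed by LOR; catheter would not advance. Keep no plateau and no LOR as separate codes, because repeats in Phase B are by LOR.
- **Reporting.** Report identification separately from catheter placement in each phase. In Phase B, keep identification by the instrument apart from identification on an LOR repeat.

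The cost is a few sentences of protocol text and slightly more recording at the bedside.
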